10.9 Appendix 9: Algorithm for Assessing Out of Range Laboratory Values

For all laboratory values obtained at prestudy (screening) visit and/or predose evaluation:

- A. If all protocol-specified laboratory values are normal, the participant may enter the study.
- B. If a protocol specified laboratory value is outside of the parameter(s) outlined in the inclusion/exclusion criteria (including a repeat if performed), the participant will be excluded from the study.
- C. If ≥ 1 protocol-specified laboratory value not specified in the inclusion/exclusion criteria is outside the normal range, the following choices are available:
 1. The participant may be excluded from the study;
 2. The participant may be included in the study if the abnormal value(s) is not clinically significant (NCS) (the investigator must annotate the laboratory value "NCS" on the laboratory safety test source document).
 3. The participant may be included in the study if the abnormality is consistent with a pre-existing medical condition which is not excluded per protocol (eg, elevated eosinophil count in a participant with asthma or seasonal allergies), the medical condition should be annotated on the laboratory report.

OR

4. The abnormal test may be repeated (refer items a. and b. below for continuation of algorithm for repeated values).
 - a. If the repeat test value is within the normal range, the participant may enter the study.
 - b. If the repeat test value is still abnormal, the study investigator will evaluate the potential participant with a complete history and physical examination, looking especially for diseases that could result in the abnormal laboratory value in question. If such diseases can be ruled out, and if the abnormal laboratory value is not clinically relevant, then the participant may enter the study.
- D. If there is any clinical uncertainty regarding the significance of an abnormal value, the participant will be excluded from the study.

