10.10 Appendix 10: Hemodynamic Stopping Criteria

Hemodynamic stopping criteria

Individual stopping criteria

During any of the treatment periods, if a particular participant demonstrates a **sustained change** (defined below) in any *one* of the following parameters, that participant will not participate in additional dose escalation. For assessing change from baseline, post-dose values will be compared to the Day 1 predose baseline established by 3 semi-recumbent measurements of heart rate and blood pressure obtained ~1-2 minutes apart within 3 hours prior to dosing.

Participants meeting individual hemodynamic stopping criteria may be re-challenged in this study only after consultation or discussion between the primary investigator and the sponsor.

During any of the treatment periods if a particular participant demonstrates change in any *one* of the following parameters lasting ≥ 90 minutes, dose escalation in that participant will be halted and the participant may be withdrawn from the study or re-challenged at the same dose or at a lower dose. Participants that meet criteria listed below will be followed up until parameters no longer meet stopping rule criteria. Each participant will individually define his limit for continuation. Stopping rules will apply for a particular participant when he demonstrates a **sustained change** (at least 4 triplicate measurements or at least 1 triplicate measurement every 30 min of which the median result of each triplicate measurement will account for checking the stopping criteria) of ≥ 90 minutes in any *one* of the following criteria during the postdose period:

Heart rate:

- 1) Resting HR increase over the predose baseline of ≥ 25 bpm.
- 2) Resting HR > 120 bpm

Blood pressure:

- 1) Resting SBP reduction > 25 mmHg over the predose baseline.
- 2) Resting SBP < 90 mmHg or participant placed in the Trendelenburg position.
- 3) Resting SBP ≥ 180 mmHg
- 4) Resting DBP < 50 mmHg or DBP ≥ 110 mmHg

Blood pressure and heart rate:

- 1) For any participants: > 20 mmHg drop in resting SBP and > 20 bpm rise in resting HR
- 2) For any participants: > 30 mmHg drop in orthostatic SBP and > 30 bpm rise in orthostatic HR

Definitions for HR and BP

Participants must be resting and semirecumbent for *at least* 10 minutes prior to obtaining *any* measurements used to limit dose escalation (except for changes noted while obtaining orthostatic signs).

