Baseline HR and BP: Predose baseline values will be determined for each specific period. For the investigator, the baseline will be calculated using the median from the triplicate measurements obtained approximately 1-2 minutes apart within approximately 3 hours prior to dosing to determine that change from baseline. For all formal statistical testing, the mean baseline will be used to calculate the change from baseline.

Sustained changes are defined as lasting greater than or equal to 90 minutes. If any of the resting, semi-recumbent or orthostatic parameters defined above are exceeded, that participant must remain resting and semi-recumbent for at least the next 90 minutes. During that time, BP (systolic and diastolic) and HR will be obtained every 30 minutes (i.e., at 30, 60, and 90 minutes following). If a participant's BP (systolic *or* diastolic), *or* heart rate exceeds the parameters for the median of *all three* of the following three 30-minute periods, this is defined as a sustained finding, and dosing will end for that particular participant. Following 90 minutes, if, in the opinion of the investigator, the participant requires further observation, the participant will remain resting and semi-recumbent until HR and/or BP return to baseline. For HR and BP that are out of range, if the recheck is within normal range this is not considered a sustained change.

Notes

If an assessment of the present and previous periods raises safety and tolerability concerns though individual participant/participants do *not* meet the criteria described above, and after discussion with the investigator and the Merck monitor, dose escalation for the entire panel may end.

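### Appendix 10 closes its sustained-change definition with an undefined normal range, which conflicts with the rule above it and, read as an absolute range, can clear a participant who still breaches a change-from-baseline criterion

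*Combined protocol and SAP*

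**What the plan says.** For individual hemodynamic stopping, Section 6.6.1 gives no limits of its own and refers to Appendix 10. That appendix lists two kinds of resting limit.

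- Absolute limits, including HR above 120 bpm and SBP below 90 mmHg.
- Changes from the predose baseline: "Resting HR increase over the predose baseline of ≥ 25 bpm"; "Resting SBP reduction > 25 mmHg over the predose baseline"; and the combined criterion, "For any participants: > 20 mmHg drop in resting SBP and > 20 bpm rise in resting HR".

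There is also an orthostatic criterion. Triplicate readings are taken, "of which the median result of each triplicate measurement will account for checking the stopping criteria". Under the definitions for HR and BP, crossing a limit starts at least 90 minutes of semi-recumbent rest with rechecks at 30, 60 and 90 minutes. If the medians at all three still exceed the limits, "this is defined as a sustained finding, and dosing will end for that particular participant". Two sentences later the paragraph ends: "For HR and BP that are out of range, if the recheck is within normal range this is not considered a sustained change".

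The protocol gives no normal range for HR or BP. It uses the term for hemoglobin (Section 5.1, criterion 11), lung function (Section 5.2, criterion 11, and Section 8.3.5) and laboratory values, as in Appendix 9: "If the repeat test value is within the normal range, the participant may enter the study".

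**The concern.** The paragraph contains two tests for the same decision. The operative rule asks whether the recheck medians still meet the stopping criteria. The closing sentence asks whether the recheck is normal, and it does not say which recheck counts.

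The tests agree for the absolute limits if the range is taken to be those limits. They can disagree for the change-from-baseline criteria, because a value can sit inside an absolute range and still be far from that participant's own baseline. A clinician at the bedside would naturally take a normal range for HR or BP to be an absolute one. What is at stake is a single safety decision: whether that participant's dosing stops, and whether the investigator and sponsor must confer before any re-challenge.

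**Working it through.** **Inputs.** The change criteria are those of Appendix 10: SBP fall above 25 mmHg; HR rise of at least 25 bpm; combined fall above 20 mmHg with rise above 20 bpm. Because the protocol defines no normal range, the range is an assumption. Three sets of limits that stand in the protocol were tried: the absolute stopping limits (Appendix 10), the same-day discharge limits (Section 8.1.11) and the limits in exclusion criterion 22 (Section 5.2). Values are whole numbers.

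**Formulas.** Let L be the lowest in-range SBP, U the highest in-range HR, b the baseline and v the recheck.

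- SBP fall: v ≥ L and b − v > 25 together require b ≥ L + 26.
- HR rise: v ≤ U and v − b ≥ 25 together require b ≤ U − 25.
- Combined: baseline SBP ≥ L + 21 and baseline HR ≤ U − 21.

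**Baselines at which an in-range recheck can still breach a change criterion.**

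| Assumed range | SBP fall | HR rise | Combined |
|---|---|---|---|
| SBP ≥90, HR ≤120 (absolute stopping limits) | SBP ≥116 | HR ≤95 | SBP ≥111 and HR ≤99 |
| SBP ≥90, HR <110 (discharge) | SBP ≥116 | HR ≤84 | SBP ≥111 and HR ≤88 |
| SBP ≥100, HR ≤100 (exclusion 22) | SBP ≥126 | HR ≤75 | SBP ≥121 and HR ≤79 |

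The width of the gap depends on the range. At baseline SBP 140, in-range rechecks that still breach run from 90 to 114 under the absolute limits and from 100 to 114 under exclusion 22. At baseline SBP 120 they run from 90 to 94 under the absolute limits, and there are none under exclusion 22. At baseline HR 70 they run from 95 to 120 under the absolute limits and from 95 to 100 under exclusion 22. At baseline HR 80 they run from 105 to 120 under the absolute limits, and there are none under exclusion 22.

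**Hypothetical cases.** In each, the first post-dose reading is out of range, as the sentence requires.

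1. Baseline SBP 140, post-dose 85, rechecks 108, 108, 108. The fall is 140 − 108 = 32 > 25 each time. The all-three rule says sustained; the closing sentence, read literally, says not sustained. This holds under all three ranges.
2. Baseline SBP 140 and HR 70, post-dose 88 and 112, rechecks 117 and 93 three times. The fall is 140 − 117 = 23 and the rise is 93 − 70 = 23. Neither single change criterion is met (23 is not above 25, and 23 is below 25), but the combined criterion is met at every recheck. This also holds under all three ranges.

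Exclusion 22 admits Period 1 baselines of SBP ≥100 and HR ≤100. Under the widest range, therefore, Period 1 SBP baselines of 100 to 110 carry no SBP or combined gap, and HR baselines of 96 to 100 carry no HR-rise gap.

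**The case against.** The strongest reply is that context settles the meaning. The recheck is triggered by exceeding the listed limits, the test is exceeding them three times, and follow-up runs until the stopping criteria are no longer met. Appendix 10 also says that each participant sets his own limit for continuing, which points away from a population range. On that view the closing sentence only restates that one compliant recheck breaks the sequence. The gap appears only if the absolute limits are taken as the range and the change limits are left out. This is persuasive as to intent, but the sentence does not say it.

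The backstops are real. Investigator and sponsor review vital signs and other safety data before Periods 2 and 3 (Section 8.11.2), and escalation decisions use vital signs (Section 6.6). The investigator may discontinue a participant for any untoward effect (Section 7.1). The notes in Appendix 10 allow escalation to end for a whole panel even when no individual criterion is met. A stop is also not always final: after discussion with the sponsor, "the participant may be withdrawn from the study or re-challenged at the same dose or at a lower dose". Panel D steps down from 480 to 120 µg, and Section 4.3.3 describes dosing up to 360 µg in Panels B and C in the past tense, so few upward steps may remain. These points limit the consequence but do not remove the contradiction. A wrongly cleared participant after 480 µg would not trigger the consultation that Appendix 10 requires before re-challenge.

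A reader might infer that the trial lacks a working hemodynamic stop, or that participants have been wrongly cleared. The documents support neither. The all-three rule is explicit and correct, and Section 4.3.2 reports no effect on HR or BP so far in any clinical study of the compound.

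**Conclusion.** The inconsistency holds. It is a wording error in a safety rule, not a flaw in the design. The operative rule gives the right test; the closing sentence adds an undefined second one that can contradict it for the SBP-fall, HR-rise and combined resting criteria.

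The size depends on an assumed range: baseline SBP of at least 116 or HR of at most 95 under the widest range tried, and at least 126 or at most 75 under the narrowest. These thresholds show where a conflict is possible, not how often it would occur. The documents give no distribution of baseline or post-dose values, so the number of participants affected cannot be computed. No endpoint, sample size or analysis depends on the sentence. It is worth correcting because it sits in the rule that ends an individual's dosing.

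**What to change.** Replace the closing sentence with:

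> *A change in a given resting criterion is not considered sustained if the median at any of the 30-, 60- or 90-minute rechecks no longer meets that criterion; each resting criterion, including the change-from-baseline and combined criteria, is judged separately.*

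In case 1 the SBP-below-90 criterion would then be cleared and the SBP-fall criterion would stand. In case 2 the combined criterion would stand. The text is limited to resting criteria because participants stay semi-recumbent during the rechecks, so the orthostatic criterion cannot be retested then.

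The cost is one sentence in Appendix 10, with no new measurements and no change to the analysis. Slightly more participants may meet the stop than under the normal-range reading. A participant who breaches different criteria at different rechecks, but no single one at all three, would not be stopped by this rule. That fits Appendix 10's requirement of a sustained change in any one criterion, and the discretionary safeguards still apply.

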10.11 Appendix 11: Guidelines for the Treatment of Hypo/Hypertension

The following is guidance for the investigator with the understanding that the investigator must always use his/her own clinical judgment in carrying out this guidance and/or deviating from them, with a principle focus on ensuring the safety of study participants.

Severe Hypotension

In the event that a participant develops severe hypotension (systolic blood pressure <80 with or without symptoms or <90 accompanied by symptoms) the following is suggested:

- Participant may be placed in the Trendelenburg position (supine with head downward/feet elevated above the heart).
- Intravenous access should already be in place.
- Bolus intravenous normal saline as appropriate until SBP is >100 mmHg or until symptoms resolve.
- The participant should be frequently monitored for HR and BP.
- The participant should be rapidly evaluated. Evaluations will include a physical examination. 12-lead ECG and laboratory safety panel may be performed at the discretion of the investigator.
- If/when appropriate, efforts should be made to ensure the participant has two functioning and open intravenous access sites.
- If participant remains hypotensive and/or there has been no resolution of any associated symptoms despite the above, the participant should be rapidly transferred to a location where definitive care (i.e., an Emergency or Intensive Care Unit) is available.

Severe Hypertension

In the event that a Participant develops severe hypertension (systolic blood pressure >170 mmHg and/or diastolic blood pressure >105 mmHg) the following is suggested:

- Participant should be placed in a semi-recumbent position.
- Intravenous access should already be in place in the participant.
- The participant should be frequently monitored for HR and BP until BP returns to baseline.
- The participant should be rapidly evaluated. Evaluations will include a physical examination. 12-lead ECG and laboratory safety panel may be performed at the discretion of the investigator.

- Treatment should be considered per local standards, based upon the degree of hypertension and/or presence/absence of symptoms (e.g., headache, evidence of heart failure or coronary insufficiency).
- Blood pressure should be reduced within a few hours.

Participants who are symptomatic or with evidence of end-organ damage should be rapidly transferred to a location where definitive care (i.e., Emergency Room or Intensive Care Unit) is available.

10.12 Appendix 12: Abbreviations

Abbreviation	Expanded Term
AE	adverse event
BDS	blood drug screen
BP	Blood pressure
CI	Cardiac index
CO	Cardiac output
CRF	Case Report Form
CRU	clinical research unit
CT	computed tomography
DILI	drug-induced liver injury
DLCO	Diffusing capacity of the lung for carbon monoxide
DNA	deoxyribonucleic acid
ECG	electrocardiogram
ECI	event of clinical interest
eCRF	electronic Case Report Form
EDC	electronic data collection
EMA	European Medicines Agency
ERA	Endothelin receptor antagonist
FDAAA	Food and Drug Administration Amendments Act
FEV1	forced expiratory volume in 1 second
FRC	functional respiratory capacity
FSH	Follicle stimulating hormone
FVC	forced vital capacity
GCP	Good Clinical Practice
Hgb	hemoglobin
HR	Heart rate
IB	Investigator's Brochure
ICF	Informed Consent Form
ICH	International Conference on Harmonization
IEC	Independent Ethics Committee
IRB	Institutional Review Board
IUD	intrauterine device
MVO ₂	mixed venous oxygen saturation
MTD	maximum tolerated dose
NOAEL	no observed adverse effect level
PAH	pulmonary arterial hypertension
PAP	pulmonary artery pressure
PAWP	Pulmonary artery wedge pressure
PBO	placebo
PBV	pulmonary blood volume
PDE5i	Phosphodiesterase type 5 inhibitor
PEF	peak expiratory flow
PFT	pulmonary function tests
PK	pharmacokinetic
PT	prothrombin time
aPTT	activated partial thromboplastin time
PVR	Pulmonary vascular resistance
QP2	department of quantitative pharmacology and pharmacometrics
RAP	Right atrium pressure
RHC	Right heart catheterization
RNA	ribonucleic acid

Abbreviation	Expanded Term
RR	respiratory rate
RV	residual volume
RVSP	right ventricular systolic pressure
RVEDP	right ventricular end diastolic pressure
SAC	Scientific Advisory Committee
SAE	serious adverse event
sGC	Soluble guanylate cyclase
SoA	schedule of activities
SVR	Systemic vascular resistance
SUSAR	suspected unexpected serious adverse reaction
TEMP	temperature
TLC	Total lung capacity
UDS	urine drug screen
VC	Vital capacity
WOCBP	woman/women of childbearing potential
WONCBP	Woman/women of non-childbearing potential

